To evaluate the maintenance of effect of tralokinumab in combination with TCS when used to treat moderate to severe AD for 32 weeks for subjects achieving clinical response at Week 16.	 IGA of 0/1 at Week 32 among subjects with IGA of 0/1 at Week 16 after initial randomisation to tralokinumab. EASI75 at Week 32 among subjects with EASI75 at Week 16 after initial randomisation to tralokinumab. 	
Other objectives	Other endpoints	
To evaluate the efficacy over time of tralokinumab in combination with TCS on severity and extent of AD, itch, and health related quality of life compared with placebo in combination with TCS.	 IGA 0/1 at each scheduled assessment until Week 14. EASI75 at each scheduled assessment until Week 14. Change in SCORAD from baseline to each scheduled assessment until Week 14. Change from baseline to each scheduled assessment through Week 4 to 14 in Worst Daily Pruritus NRS (weekly average). Reduction of Worst Daily Pruritus NRS (weekly average) of at least 4 from baseline to each scheduled assessment through Week 4 to 14. Change in DLQI score from baseline to each scheduled assessment until Week 14. 	

Trial ID: LP0162-1339	Date: 29-Aug-2018	Version: 4.0
		Page 34 of 129

To evaluate the efficacy of tralokinumab in combination with TCS on patient-reported outcomes compared with placebo in combination with TCS.

- Change in Eczema-related Sleep NRS (weekly average) from baseline to Week 16.
- Reduction of Worst Daily Pruritus NRS (weekly average) of at least 4 from baseline to Week 2.
- Change in Worst Daily Pruritus NRS (weekly average) from baseline to Week 2.
- Reduction of Worst Daily Pruritus NRS (weekly average) of at least 3 from baseline to Week 16.
- Reduction of Worst Daily Pruritus NRS (weekly average) of at least 3 from baseline to Week 2.
- Change in POEM score from baseline to Week 16.
- Reduction from baseline to Week 16 of POEM score ≥4 points in subjects with baseline POEM score >4.
- Change in EQ-5D-5L from baseline to Week 16.
- Change in HADS from baseline to Week 16.
- HADS anxiety and HADS depression subscale scores <8 at Week 16 in subjects with baseline HADS anxiety or HADS depression subscale scores ≥8.

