12.3.4 Multiple testing procedure

To control the overall type 1 error rate, the primary analyses of the primary estimands for the primary and secondary endpoints for the initial treatment period will follow the hierarchical testing procedure outlined in Panel 11. The hypothesis relating to a specific endpoint cannot be rejected unless all hypotheses relating to endpoints earlier in the hierarchy are also rejected.

Trial ID: LP0162-1339	Date: 29-Aug-2018	Version: 4.0
		Page 86 of 129

Panel 11 Testing procedure for primary and secondary endpoints

 $Arrows \, indicate \, order \, of \, testing \, when \, superiority \, is \, shown \, for \, an \, endpoint \, within \, a \, box.$

Abbreviations: DLQI, Dermatology Life Quality Index; EASI75, at least 75% reduction in Eczema Area and Severity Index score; IGA, Investigator's Global Assessment.

The procedure will be as follows:

IGA 0/1 at Week 16 between tralokinumab+TCS and placebo+TCS will be evaluated at a 5% significance level. If the test is significant, EASI75 at Week 16 between tralokinumab+TCS and placebo+TCS will be evaluated at a 5% significance level.

If both these tests are significant, the 5% significance level (alpha) will be propagated to the three secondary endpoints: SCORAD at Week 16, Pruritus at Week 16, and DLQI at Week 16. The evaluations of the three secondary endpoints between tralokinumab+TCS and placebo+TCS will use the Holm method (35) for 3 ordered p-values at a 5% significance level to adjust for multiplicity.

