12.3.5.1 Primary estimand: 'composite'

The primary estimand for the primary endpoints will be:

• Treatment difference in response rates of IGA 0/1 and EASI75 after 16 weeks achieved without rescue medication, regardless of treatment discontinuation.

The primary estimand assesses the expected difference in response rates (defined as response obtained without initiation of any rescue medication) after 16 weeks, resulting from initiation of a treatment regimen with tralokinumab+TCS compared to a treatment regimen with placebo+TCS.

Primary analysis for the primary estimand

Data retrieved at Week 16 for subjects who have permanently discontinued IMP prior to Week 16 will be included in the analysis. Subjects who prior to the Week 16 visit have received rescue medication will be considered non-responders, reflecting an assumption that initiation of rescue medication indicates failure of the randomised treatment to achieve response, and that a (possible) observed positive response after initiation of rescue medication is not attributable to the randomised treatment. Missing data for subjects who do not attend the Week 16 visit and where rescue medication has not been used prior to Week 16, will be imputed as non-responders.

The difference in response rates between treatment groups will be analysed using the Cochran-Mantel-Haenszel test stratified by region (Europe and North America) and baseline

Trial ID: LP0162-1339	Date: 29-Aug-2018	Version: 4.0
		Page 88 of 129

disease severity (IGA 3 or 4). The treatment estimate and the corresponding 95% CI will be presented. The null hypothesis of no difference in response rates between tralokinumab+TCS and placebo+TCS will be tested against the 2-sided alternative that there is a difference.

The primary endpoints will be tested sequentially at a 5% significance level. IGA 0/1 will be tested first, and, if significant, then EASI75 will be tested. If both primary null hypotheses are rejected, the secondary endpoints will be tested.

Sensitivity analyses for the primary estimand

Two sensitivity analyses are specified for the primary estimand. In both cases the same Cochran-Mantel-Haenszel test as used for the primary analysis will be applied including stratification by region and baseline disease severity.

The purpose of the analyses is to assess the robustness of results of the primary analysis with respect to the retrieved data at Week 16 and assumptions regarding missing Week 16 data.

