12.3.7 Analysis of additional secondary endpoints

Initial treatment period

The analysis of the below additional secondary endpoints will be based on the primary analyses of the primary estimand as specified above for the relevant primary dichotomous endpoints and continuous secondary endpoints, respectively.

The following dichotomous additional secondary endpoints will be analysed according to the primary analysis of the primary estimand for the primary endpoints:

- EASI50 at Week 16.
- EASI90 at Week 16.
- SCORAD50 at Week 16.
- SCORAD75 at Week 16.
- Reduction from baseline (Y/N) of DLQI of ≥4 points (in subjects with baseline DLQI ≥4) at Week 16.

The change from baseline to Week 16 in EASI score and the change from baseline to Week 16 in Worst Daily Pruritus NRS weekly average will be analysed according to the primary analysis of the primary estimand for the continuous secondary endpoints.

To evaluate the efficacy related to health care resource utilisation, the amount of TCS used (assessed as the amount of TCS used between visits), and the number of days without topical treatment use (collected as Patient Days of Topical Treatment Use in the eDiary) will be determined by 2-week periods. The amount of TCS used and the number of days without topical treatment use will each be analysed by a repeated measurements model with an unstructured covariance matrix and the mean modelled as follows:

 $Y = treatment \times visit + region + baseline IGA$

Results obtained after initiation of rescue treatment will be excluded from the analyses.

AD flares will be summarised descriptively as the proportion of subjects having had AD flares at Week 16, the number of AD flares from baseline to Week 16, and the rate of AD flares from baseline to Week 16. The rate of AD flares will be defined as the number of AD flares divided by time at risk, where the time at risk for each subject is the time from treatment start to last visit attended up to Week 16.

Trial ID: LP0162-1339	Date: 29-Aug-2018	Version: 4.0
		Page 97 of 129

Continuation treatment period

To support the maintenance objective of the trial, IGA of 0/1 at Week 32 among subjects with IGA of 0/1 at Week 16 and EASI75 at Week 32 among subjects with EASI75 at Week 16, both after initial randomisation to tralokinumab, will be summarised descriptively by treatment group of the continuation treatment period.

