12.3.8.2 Patient-reported outcomes

The PROs POEM, DLQI, EQ-5D-5L, and HADS will be summarised by treatment group and visit using descriptive statistics. The summaries will be made separately for initial treatment and continuation treatment. Data from the initial treatment period will be presented for the full analysis set and data from the continuation treatment period will be presented for the continuation treatment analysis set.

The PROs collected daily in the eDiaries (Worst Daily Pruritus NRS, Average Daily Pruritus NRS, Eczema-related Sleep NRS, PGI-B, and PGI-S) will all be summarised over time by treatment group using descriptive statistics. The summaries will be separate for initial treatment and continuation treatment. Data from the initial treatment period will be presented for the full analysis set and data from the continuation treatment period will be presented for the continuation treatment analysis set.

The Average Daily Pruritus NRS collected over the last week prior to baseline (Day -6 to 0) will be used to calculate the baseline average daily itch. A minimum of 4 Average Daily Pruritus NRS scores out of the 7 days is required to calculate the baseline average score.

To investigate a possible early onset of itch relief, a reduction in Worst Daily Pruritus NRS weekly average of at least 4 from baseline to Week 2 as well as a reduction of at least 3 from baseline to Week 2 will be summarised by treatment group. Furthermore, to investigate itch relief during initial treatment a reduction in Worst Daily Pruritus NRS weekly average of at least 3 from baseline to Week 16 will be summarised. These three endpoints will each be analysed according to the primary analysis of the primary estimand for the dichotomous primary endpoints.

In the subgroup of subjects with either HADS anxiety or HADS depression subscale score ≥8 at baseline, the proportion of subjects with both HADS anxiety and HADS depression subscale score <8 at Week 16 will be summarised by treatment group and analysed as described for the primary analysis of the primary estimand for the primary endpoints.

In the subgroup of subjects with a baseline POEM score \geq 4, the proportion of subjects with a reduction in POEM score \geq 4 at Week 16 will be summarised by treatment group and analysed as described for the primary analysis of the primary estimand for the primary endpoints.

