The change from baseline to Week 2 in Worst Daily Pruritus NRS weekly average, and the change from baseline to Week 16 in Eczema-related Sleep NRS weekly average, HADS, POEM, and the EQ-5D-5L index will be summarised by treatment group and domain, where

Trial ID: LP0162-1339	Date: 29-Aug-2018	Version: 4.0
		Page 99 of 129

applicable, and analysed according to the primary analysis of the primary estimand for the continuous secondary endpoints. For the Eczema-related Sleep NRS score, the mean over the last 7 days prior to randomisation (Day -6 to 0) will be used as the baseline value.

For the PGI-B, a day of 'no or slight bother' is defined as answering the question with "not at all" or "slightly". The subjects' number of days of 'no or slight bother' will be tabulated per treatment group for the initial treatment period. The mean number of days will be presented with 95% CIs and compared between the 2 treatment groups using an analysis of variance model including treatment, region, and baseline IGA as factors.

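### The HADS below-8 responder analysis ignores baseline HADS and so gives up precision; its absolute rates should be read only as a between-arm difference (minor)

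*Protocol*

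**What the plan says.** Section 6, Panel 4 lists the endpoint under other endpoints: "HADS anxiety and HADS depression subscale scores <8 at Week 16 in subjects with baseline HADS anxiety or HADS depression subscale scores ≥8". Section 12.3.8.2 sets the population ("In the subgroup of subjects with either HADS anxiety or HADS depression subscale score ≥8 at baseline") and the response ("the proportion of subjects with both HADS anxiety and HADS depression subscale score <8 at Week 16"), and sends the analysis to the primary analysis of the primary estimand for the primary endpoints.

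That analysis, in Section 12.3.5.1, is a "Cochran-Mantel-Haenszel test stratified by region (Europe and North America) and baseline" disease severity (IGA 3 or 4). Rescue before Week 16 counts as non-response, and missing Week 16 data "will be imputed as non-responders". Baseline HADS does not appear.

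Two further provisions bear on the point:

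- Section 12.3.4 limits type I error control to the primary and secondary endpoints ("the primary analyses of the primary estimands for the primary and secondary endpoints for the initial treatment period will follow the hierarchical testing procedure"), so this endpoint lies outside it.
- Section 12.3.8.2 also plans a continuous analysis: "HADS, POEM, and the EQ-5D-5L index will be summarised by treatment group and domain", using the repeated measurements model of Section 12.3.6.1. That model contains baseline value by visit.

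**The concern.** The value 8 both selects the subjects and defines response, on one reading each time. A subject just above the cut-off at baseline can therefore become a responder through a small movement, provided the other subscale is also below 8. A subject well above it almost never can without real change. Baseline HADS thus explains much of the variation in the outcome.

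Leaving it out has two consequences. The estimated risk difference is noisier than it need be, in a subgroup that is only part of the 369 subjects. And part of the response rate in each arm reflects regression to the mean, so a rate quoted alone could be misread as the share of subjects whose anxiety or depression resolved.

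**Working it through.** **The plan's own figures.** There is none for this endpoint: no HADS mean, SD, reliability, subgroup size, effect or power. The only power figures, in Section 12.1, reproduce. For IGA 0/1 at 30% v 15% with 246 v 123:

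- pooled rate = (246 × 0.30 + 123 × 0.15)/369 = 0.25
- SE under the null = √[0.25 × 0.75 × (1/246 + 1/123)] = 0.0478
- SE under the alternative = √[0.30 × 0.70/246 + 0.15 × 0.85/123] = 0.0435
- power = Φ[(0.15 − 1.96 × 0.0478)/0.0435] = Φ(1.29) = 90%

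EASI75 at 40% v 15% gives 99.96%, against the stated >99.9%.

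**Assumptions for HADS (none from the protocol).** Subscale SD 4; baseline means (anxiety/depression) 6/4, 7/5 or 8/6; true-score correlation 0.7; independent visit error; scores rounded and held to 0-21. The 0-21 range does follow from Section 10.3.2.10 (7 items scored 0-3). Under such values roughly 150-235 of the 369 subjects enter the subgroup.

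**Step 1: how far baseline HADS predicts crossing.** Take one subscale with mean 7, SD 4 and reliability 0.85, and no true change. Given a first score x, the second has mean 7 + 0.85(x − 7) and SD 4 × √(1 − 0.85²) = 2.11. A recorded score below 8 means a value below 7.5.

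- x = 8: mean 7.85; Φ[(7.5 − 7.85)/2.11] = Φ(−0.17) = about 43%
- x = 12: mean 11.25; Φ[(7.5 − 11.25)/2.11] = Φ(−1.78) = about 4%

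This one-subscale approximation ignores the second subscale, but it shows the gradient that the CMH test leaves unexplained.

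**Step 2: crossing with no true change, both subscales.** Simulating the full rule with reliability 0.6-0.9, 11-32% of the subgroup end below 8 on both subscales (17% at means 7/5, reliability 0.85). Among subjects whose highest baseline subscale is 8-9, the share is 27-45%. A wider grid of means (5-8 and 3.5-6.5) and SDs (3.5-4.5), with correlation 0.6 and reliability 0.7-0.9, gives 10-35%. Rescue and missing data are not modelled in these figures; counting them as non-response would lower observed rates in both arms.

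**Step 3: planned test against baseline adjustment, same binary endpoint.** Trials of 246 v 123 were simulated with a 1.5-point true benefit and reliability 0.7-0.85. The stratified CMH test was compared with logistic regression that also contains the two baseline subscales.

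| Quantity | Result |
|---|---|
| Gain in power from adjustment | about 5-13 points, in every scenario |
| Variance ratio of the risk difference, CMH to adjusted | 1.13-1.43 |
| Mean risk difference | the same for both |
| Type I error | near 5% |

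The pattern held when rescue or missing data were counted as non-response. The variance ratio corresponds to 13-43% more subjects, in round terms 13-40%.

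Worked example (means 7/5, reliability 0.85): CMH power 79.8%, adjusted 92.3%, a gain of 12.5 points. The SD of the estimate is 0.0640 v 0.0563, and (0.0640/0.0563)² = 1.29. This case lies towards the upper end of the range of gains.

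**Step 4: other remedies for comparison.** Changing the response rule does not give a dependable gain. Adding a fall of at least 3 points gave 78% v 81% in one set of runs and gains of 0 to 11 points in another. A fall of at least 4 gave −7 to +9 points, and confirmation at a second visit 0 to about 9.

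**The case against.** The case for leaving the text alone has real weight.

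- **Tier.** This is an 'other' endpoint, outside the hierarchy, with no power claim attached. That stands and limits the severity.
- **A baseline-adjusted HADS analysis already exists.** The planned repeated measurements analysis of HADS change uses the size of the change and conditions on baseline. That also stands. It covers the full analysis set rather than the raised-score subgroup, and targets the hypothetical rather than the composite estimand, so it complements the responder analysis without making it more precise.
- **Consistency.** The same CMH test, without the baseline score, serves all the binary endpoints, and a common method is a fair design choice. A departure here costs some uniformity, though both subscales are already collected at Week 0.
- **A threshold-status endpoint is legitimate.** The DLQI endpoint, "Reduction from baseline (Y/N) of DLQI of ≥4 points (in subjects with baseline DLQI ≥4) at Week 16", measures change; HADS below 8 measures status. The lack of a minimum change is not an error.

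A reader might go further and infer that the treatment comparison is biased. It is not: chance crossings arise in both randomised arms, and the placebo arm shows the background rate. A reader might also blame lost power on the missing minimum change or confirmation; Step 4 does not bear that out. Only the covariate adjustment gives a consistent gain.

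**Conclusion.** The point holds as a minor matter of precision and presentation. The protocol fixes a test for the HADS responder endpoint that ignores a strong predictor it already collects. Under the assumptions listed, adjustment recovers about 5-13 points of power, equivalent to roughly 13-40% more subjects, with type I error near 5% and the same mean risk difference.

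The 11-32% no-change crossing range must not be taken as a property of this trial. It rests wholly on assumed means, SD, correlation and reliability. It supports caution with the absolute rates and nothing stronger. Nor do the documents support saying that HADS is analysed without baseline adjustment altogether; that is true of this binary analysis only.

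**What to change.** In Section 12.3.8.2, or in the statistical analysis plan update that Section 12.3.12 places before unblinding, state that the HADS below-8 endpoint will be analysed by logistic regression on treatment, region, baseline IGA and the two baseline HADS subscale scores. Report it as a standardised risk difference with 95% CI, and keep the composite rules for rescue and missing data. Add that the response rates are to be read as a between-arm difference, beside the planned continuous HADS change.

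A supportive definition that also requires a fall of at least 3 points on each subscale raised at baseline is optional. At means 7/5 and reliability 0.85 it cuts the no-change rate from 17% to 9%, but it is not needed for the power gain.

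The cost is a sentence or two of text and no new data. The one drawback is that this endpoint's model would differ from the common CMH test.

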Vital signs	X		X	X ⁴	10.4.1
Physical examination	X		X	X ⁴	10.4.2
EGGs	X		X	X ⁴	10.4.3
Urine pregnancy test	X		X	X ⁴	10.4.4
Serum chemistry, haematology, IgE	X		X	X ⁴	10.4.5
Urinalysis	X		X	X^4	10.4.5
Pharmacokinetics	X		X	X^4	10.4.6
Anti-drug antibodies	X		X	X ⁴	10.4.7
Adverse events	X	X	X	X ⁴	11, Appendix 1, Appendix 2

- Subjects will have a final safety follow-up visit 16 weeks after the last dose of IMP (which is also considered end of trial visit), except subjects who enter the long-term extension trial (conducted under a separate protocol [LP0162-1337, ECZTEND]) for whom the end of trial visit will be the last visit in the present trial before transfer to ECZTEND.
- 2) Subjects who permanently discontinue IMP prior to Week 16 will also attend the nominal Week 16 visit (visit 11x).
- 3) Assessments and procedures performed at Week 16 (see Panel 2) are also to be done at an early termination visit.
- 4) Assessments and procedures to be performed at an unscheduled visit are left at the investigator's discretion; except if due to atopic dermatitis flares, then as a minimum IGA, EASI, concomitant medications/procedures, and AEs are to be assessed.
- 5) eDiary includes: Eczema-related Sleep NRS, Worst Daily Pruritus NRS, Average Daily Pruritus NRS, Days of Topical Treatment Use, Patient Global Impression of Bother, and Patient Global Impression of Severity; subjects will complete daily (Week -2 to 32). Subjects who permanently discontinue IMP prior to Week 16 will complete the eDiary daily until the Nominal Week 16 visit.

Abbreviations: DLQI, Dermatology Life Quality Index; EASI, Eczema Area and Severity Index; ECG, electrocardiogram; eDiary, electronic diary; EQ-5D 5L, EuroQoL 5-Dimension Health Questionnaire 5 Level; HADS, Hospital Anxiety and

Trial ID: LP0162-1339	Date: 29-Aug-2018	Version: 4.0
		Page 26 of 129

Depression Scale; IGA, Investigator's Global Assessment; IgE, immunoglobulin E; IMP, investigational medicinal product; NIMP, non-investigational medicinal product; NRS, numeric rating scale; POEM, Patient Oriented Eczema Measure; SCORAD, Scoring Atopic Dermatitis; SFU, safety follow-up; TCS, topical corticosteroid.

5 Introduction and rationale

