7.1 Overall trial design

Overview

This is a randomised, double-blinded, placebo-controlled phase 3 trial to confirm the efficacy and safety of tralokinumab administered on a background of TCS therapy in adult subjects with moderate-to-severe AD. The trial will consist of a screening period of 2 to 6 weeks (Weeks -6/-2 to 0), an initial treatment period of 16 weeks (Weeks 0 to 16), and a continuation treatment period of 16 weeks (Weeks 16 to 32). The primary endpoints are assessed at Week 16, and the final efficacy assessment will be performed at Week 32. An off-treatment follow-up period for the assessment of safety is also included (Weeks 32 to 46). A schematic of the trial design is provided in Panel 1.

Screening period (Week -6 to Week 0)

The screening period has a minimum duration of 2 weeks and a maximum duration of 6 weeks and includes 1 or 2 screening visits. The exact duration of the screening period for

Trial ID: LP0162-1339	Date: 29-Aug-2018	Version: 4.0
		Page 35 of 129

the individual subject depends on the length of any washout period needed, as specified in the exclusion criteria in Section 8.3 (i.e. 4 weeks prior to randomisation for systemic immunosuppressive/immunomodulating drugs, systemic corticosteroid use, or three or more bleach baths during any week within the 4 weeks; 2 weeks prior to randomisation for TCSs, TCIs, or topical phosphodiesterase 4 [PDE-4] inhibitors). If no washout or a 2-week washout period is required, screening will be reduced to 2 weeks and reduced to 1 visit (Week -2; visit 2), i.e., the 2 screening visits will be merged. Eligibility will be assessed at the (first) screening visit and on Day 0 (hereinafter "baseline") prior to randomisation.

All subjects will attend a screening visit 14 days before baseline (Week -2; visit 2) where they will receive electronic diary (eDiary) training and start the eDiary. Data entered into the eDiary during the 2 weeks before randomisation (including the data collected on the day of the baseline visit [visit 3]) will be used to calculate baseline values of the patient-reported outcomes (PROs).

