10.3.2.5 Patient Global Impression of Bother

The PGI-B is a single item designed to capture the subject's perception of how bothered they have been by their AD over the past 24 hours at the time of completion. A 5-point categorical response scale will be used ('not at all', 'slightly', 'somewhat', 'a lot', 'very much'). Subjects will complete this item as part of the eDiary each day in the morning from Week -2 (visit 2) until Week 32. The PGI-B is included in the investigator trial file.

Trial ID: LP0162-1339	Date: 29-Aug-2018	Version: 4.0
		Page 70 of 129

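### PGI-B days of no or slight bother are compared as raw counts without the baseline PGI-B that the diary collects: this loses precision and leaves the count dependent on diary completion

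*Protocol*

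**What the plan says.** In Protocol Section 12.3.8.2, "a day of 'no or slight bother' is defined as answering the question with" one of the two mildest of the five response categories. "The subjects' number of days of 'no or slight bother' will be tabulated per treatment group for the initial treatment period". Group averages, each with its confidence interval, are then "compared between the 2 treatment groups using an analysis of variance model including treatment, region, and baseline IGA as factors". The paragraph states no denominator, no minimum number of entries, no rule for unanswered days and no baseline PGI-B term.

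Four other places bear on this:

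- Section 10.3.2.5, on collection of the item: "Subjects will complete this item as part of the eDiary each day in the morning from Week -2 (visit 2) until Week 32". Section 7.1 says of the diary data from the two weeks before randomisation that they "will be used to calculate baseline values of the patient-reported outcomes (PROs").
- Section 4, Panel 3, footnote 5: "Subjects who permanently discontinue IMP prior to Week 16 will complete the eDiary daily until the Nominal Week 16 visit".
- Section 12.3.13 places the handling of missing values in the sections on the individual analyses.
- Section 12.3.12 provides for a statistical analysis plan update, finalised before the randomisation code is broken.

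**The concern.** There are two separate issues.

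The first is precision. The model adjusts for region and baseline IGA, but not for the subject's own PGI-B before treatment. The protocol treats its other continuous patient-reported outcomes differently. DLQI is analysed with its own baseline in the model (Section 12.3.6.1), and Section 12.3.8.2 sends Sleep NRS, HADS, POEM and the EQ-5D-5L index to that same model. The PGI-B baseline is already collected, so leaving it out saves nothing.

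The second is what the count measures. A good day is defined by an answer, so an unanswered day cannot be one. Taken literally, a missed day adds the same to the total as a day of severe bother, namely zero. The count therefore reflects bother and diary completion together. If completion or trial withdrawal differs by arm, part of the between-arm difference in days is not a difference in bother.

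At stake is the reading of one supportive estimate and its CI. The confirmatory tests are not affected.

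**Working it through.** **Inputs from the protocol.** The initial treatment period is 16 weeks, or 112 days (Section 7.1). Section 12.1 gives 246 and 123 subjects and a two-sided 5% level. The protocol gives no figure for the PGI-B comparison. As a check on the sample size inputs, the stated 90% power for IGA 0/1 (30% versus 15%) reproduces:

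- Pooled rate: (246 × 0.30 + 123 × 0.15)/369 = 0.25.
- SE under the null: √(0.25 × 0.75 × (1/246 + 1/123)) = 0.0478.
- SE under the alternative: √(0.21/246 + 0.1275/123) = 0.0435.
- z = (0.15 − 1.96 × 0.0478)/0.0435 ≈ 1.29, so power is 90.2%.

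**Assumed inputs.** Everything else is an assumption: daily probability p of no or slight bother, share c of days with an entry, SD of the count, and correlation ρ between baseline PGI-B and the count.

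**Effect of completion.** Expected counted days = 112 × p × c, with entries missing independently of bother.

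With no true effect (p = 0.4 in both arms):

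- Completion 80% in both arms: 35.8 versus 35.8 days, difference 0.
- Completion 85% (tralokinumab) versus 75% (placebo): 112 × 0.4 × 0.85 = 38.1 and 112 × 0.4 × 0.75 = 33.6, a spurious difference of 4.5 days.
- For p from 0.3 to 0.5 and completion gaps of 5 to 15 points: from 112 × 0.3 × 0.05 = 1.7 days to 112 × 0.5 × 0.15 = 8.4 days.

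With an SD of 30 days, the standard error is 30 × √(1/123 + 1/246) = 3.3 days. A 4.5-day artefact would then be nominally significant in about 27% of trials, or about 21% with an SD of 35.

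With a true gain of 112 × (0.5 − 0.4) = 11.2 days:

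- 80% completion in both arms: 112 × (0.40 − 0.32) = 9.0 days. This is shrinkage only.
- 75% on tralokinumab, 85% on placebo: 112 × (0.375 − 0.340) = 3.9 days.
- 85% on tralokinumab, 75% on placebo: 112 × (0.425 − 0.300) = 14.0 days.

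The distortion can therefore go either way.

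**Effect of the baseline covariate.** Residual variance is multiplied by 1 − ρ², and the equivalent sample size is 369/(1 − ρ²). The power columns are for a 10-day difference.

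| ρ (assumed) | Variance reduction | Equivalent N | Power, SD 30 | Power, SD 35 |
|---|---|---|---|---|
| 0 | 0% | 369 | 85.5% | 73.5% |
| 0.3 | 9% | 405 | 88.6% | 77.4% |
| 0.5 | 25% | 492 | 93.6% | 84.8% |

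**Would dividing by completed days settle it?** It would only if missed days are unrelated to bother. Suppose the true rate is 40% in both arms, the tralokinumab arm misses 10% of all days, and the placebo arm misses 10% of good days and 25% of bad days.

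- Raw count: 112 × 0.4 × 0.9 = 40.3 days in both arms, so no distortion.
- Proportion of completed days: tralokinumab 0.36/0.90 = 40%; placebo 0.36/(0.36 + 0.45) = 44.4%. Over 112 days that is about 5 spurious days in favour of placebo.

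**The case against.** The strongest reply has five parts.

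1. The protocol does not say that missed days count as days with bother, and handling of missed diary entries can be left to the SAP. This stands in part. A rule can still be added, but the text already fixes the outcome as a number of days and fixes the model terms. Section 12.3.13 points to the individual section for missing-value rules, and this one has none.

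2. Stopping IMP does not stop the diary, by Panel 3 footnote 5. This stands. Days are lost mainly through trial withdrawal, loss to follow-up and skipped entries. A reader might infer that every early treatment discontinuation removes days, and the documents do not support that.

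3. PGI-B is also to be summarised over time by arm, so a count driven by missing entries would not stand alone. This helps, but the section does not ask for completion by arm to be shown beside the count.

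4. Counting only documented good days resembles the primary analysis, where missing means non-response, and a proportion can itself mislead. This stands, as the last calculation shows. It is why the proportion belongs beside the count and should not replace it.

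5. Leaving out the covariate is harmless under randomisation, baseline IGA carries some of the information, and entry criteria may make good days rare at baseline. The first part is right: only precision is lost. The last is a reason to consider the mean baseline score, and it does not justify ignoring the item.

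**Conclusion.** The point holds as a minor one. On the text it is certain that the outcome is a raw count of answered days and that baseline PGI-B is collected but not in the model. The missing covariate costs precision and causes no bias. Its size depends on an unknown correlation: 9% to 25% of residual variance for ρ of 0.3 to 0.5.

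The count shrinks with missed entries and withdrawal, and may be distorted between arms if these differ by arm. The 4.5 days is an illustration that rests on assumed rates, and with equal completion there is no spurious difference.

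A reader might infer that the plan will report an effect where none exists, or that it inflates the trial's type 1 error. The documents support neither. Nothing in them suggests unequal completion, and the analysis lies outside the testing procedure in Section 12.3.4 and is not among the endpoints in Panel 4.

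**What to change.** - Add baseline PGI-B to the model as a covariate: either the mean score or the share of days with no or slight bother, over Day -6 to 0. That is the window already used for the pruritus and sleep diary baselines.
- Keep the count, and report diary completion by arm next to it.
- Add a supporting analysis of the proportion of completed days with no or slight bother. Preferably run it by 2-week period in the repeated measurements model that Section 12.3.7 uses for days without topical treatment, with the baseline PGI-B term added. That model excludes results after rescue, so say whether the supporting analysis does the same.
- State that the supporting analysis assumes missed days resemble completed days.

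The cost is a few sentences in the statistical analysis plan update before unblinding and a few lines of code. No new data are needed.
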